7.6 Subject Discontinuation and Replacement

Every Subject should remain in the study until completion of the required follow-up period. Subjects may voluntarily withdraw from the study at any time with or without reason and it will not have any negative impact on subsequent treatment. Conceivable reasons for Subject discontinuation may include, but are not limited to, the following:

- **Subject Withdrawal:** Subject participation in this clinical study is voluntary. The Subject may choose to discontinue participation (refuse all subsequent testing) at any time without loss of benefits or penalty.
- **Discontinuation:** Subject participation may be discontinued by the Subject or Investigator because of a treatment modality change, organ transplant, transfer, death or prolonged hospitalization.
- **Investigator Termination:** The Investigator may terminate the Subject's participation without regard to the Subject's consent if the Investigator believes it is medically necessary.
- Exclusion Criterion Discovered After Enrollment: A small number of Subjects may be enrolled despite meeting an exclusion criteria due to timing of study required clinical procedures. This will be documented by the study personnel on the Case Report Form (CRF), and will be considered a protocol deviation.

- Lost-to-Follow-up: If the Subject fails to complete eight consecutive treatments, regardless of whether or not they fall into a single treatment period or a total of up to eight missed treatments, consecutive or not, per period, but has not formally withdrawn from the study, he or she will be considered lost-to-follow-up. The data from this Subject is still eligible for the intent to treat dataset. Site personnel should make all reasonable efforts to locate and communicate with the Subject, at each contact time point, including:
 - A minimum of two telephone calls to contact the Subject should be attempted. Each attempt should be recorded in the Subject's medical record, including date, time, and initials of site personnel attempting the contact.
 - o If telephone calls are unsuccessful, a certified letter should be sent to the Subject.

If the above-mentioned attempts at communicating with the Subject are unsuccessful, the Subject will be considered lost-to-follow-up.

NOTE: If the Subject can be contacted, study treatments will resume at the point when the last treatment was conducted.

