APPENDIX B: SCHEDULE OF ASSESSMENTS

Assessment		Dislusis Treatment Wesle															Study Exit						
Study Period	Baseline	Run-in	Run-in In-Center Treatment Period 1						Self-Care Transition In-Home Treatment Period 2														
Study Week		1 1 2 3 4 5 6 7 8 1				1	1 2 3 4				2	3	4	5	6	7	8						
Informed Consent (≤90 days from Run-In Tx 1)	х																						
Inclusion /Exclusion Criteria Verification	х	х																					
Demographics/Medical/Vascular Access History (including assessment of historical lab values)	x																						
Physical Exam (≤90 days from Run-In Tx 1)	х																						
Concomitant Medications ¹²	х	х	х	х	х	х	х	х	х	х	Х	Х	х	Х	х	х	х	х	х	х	х	х	х
Chemistry 20 ¹³ /CMP	X ¹⁴				x				X		x						>						
CBC15	X ¹⁵				х				Х			x x											
Iron Studies (TSAT, Ferritin, Transferrin)	X ¹⁵						х								x								
Pre and Post BUN sample collection (Kt/V) ¹⁶		х	х	х	х	х	х	х	х	х	Х	Х	х	Х	х	х	х	х	х	х	х	х	
Signs and Symptoms ¹³	х	х	х	х	х	х	х	х	х	х	Х	Х	х	Х	х	х	х	х	х	х	х	х	
Subject Evaluation of Device ¹³		х	х	х	х	х	х	х	х	х	Х	Х	Х	Х	х	х	Х	Х	х	х	х	х	
Adverse Event ¹³		Х	х	х	х	х	х	х	х	х	Х	Х	Х	х	Х	Х	Х	Х	Х	х	х	х	х
Study Completion																							х

¹²Data for each of these Assessments will be recorded at every treatment.

¹³Tests will include the following: Albumin, Alkaline Phosphatase, Alanine Aminotransferase (ALT), As partate Aminotransferase (AST), Bilirubin (total and direct), Blood Glucose, Blood Urea Nitrogen (BUN), Calcium (Ca) in blood, Carbon Dioxide (Bicarbonate), Chloride, Creatinine, Phosphate in blood, Potassium in blood, Sodium in blood, and total serum protein.

¹⁴ Additional testing at baseline is not required if lab data on file is within 2 weeks of the Run-In Period and includes all protocol required tests.

¹⁵ CBC includes: White Blood Cells (WBC), Hemoglobin (HgB), Hematocrit (HCT), Mean Corpuscular Volume (MCV), and Platelets,

¹⁶ Standard Kt/V (stdKt/V) = 168*(1-exp(-Kt/V))/t/((1-exp(-t/V))/(Kt/V)+168/(N*t)-1), where: N=number of treatments / week; t= treatment time in hours

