1.1 Design and Treatment

Subjects will be enrolled in the trial for approximately 21 weeks and will use the Tablo Hemodialysis System for their dialysis treatments according to the schedule outlined in four periods as follows:

- **Run-in, In-Center** – Subjects undergo study staff administered dialysis treatment 4 times/week for 1 week In-Center.
- **Treatment 1, In-Center** – Subjects undergo study staff administered dialysis treatment 4 times/week for 32 treatments (approximately 8 weeks) In-Center. Subjects are expected to undergo no more than 4 complete treatments per week during this treatment period.
- **In-Home Transition** – Subjects undergo device training for the study, perform self-care dialysis 4 times/week for approximately 4 weeks, and are assessed for stability in the new care environment.
- **Treatment 2, In-Home** – Subjects undergo self-care dialysis treatment 4 times/week for 32 treatments (approximately 8 weeks) In-Home. Subjects are expected to undergo no more than 4 complete treatments per week during this treatment period.

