1.2 Study Procedures

Inclusion and exclusion criteria will be assessed prior to initiating the In-Center run-in period. Subjects with a diagnosis of ESRD who meet the inclusion and exclusion criteria will be eligible for participation in this study. The In-Center run-in period will take place for one week from Day -7 to Day -1.

Subjects who continue to meet the inclusion and exclusion criteria will enter the first treatment period, which consists of In-Center dialysis using the Tablo

Hemodialysis System. To be considered *enrolled* in the study, the subject must meet all inclusion and exclusion criteria and have started the first study treatment during treatment period 1. The first treatment period will start on Day 1 and continue until the subject completes 32 treatments (approximately 8 weeks, with 4 treatments/week).

Over the approximate four week In-Home transition period, investigational site personnel confirm the Subject or trained care partner is 1) stable in the new care environment, 2) has been appropriately trained on the set up and use of the Tablo Hemodialysis System, and 3) has satisfactorily completed the items of the patient skills assessment. The Subject or trained care partner will be responsible for device set up and initiating therapy under the supervision of study personnel In-Center during the first portion. The second portion of the transition period In-Home will be supervised at the discretion of the investigator.

Subjects or their trained care partner will administer dialysis therapy at home during treatment period 2 according to the investigator's instruction. This In-Home treatment period lasts a total of 32 treatments (approximately 8 weeks, with 4 treatments/week).

During each of the four periods described above, the following assessments will be performed:

- Every treatment: signs and symptoms, subject evaluation of the device, and adverse events.
- Weekly: concomitant medications and pre and post BUN sample collection,
- Monthly: Starting with the baseline evaluation, chemistry and hematology assessments will be performed approximately every four weeks. For analysis purposes, all laboratory results obtained during the baseline evaluation will be considered as the baseline measurements.

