^a Treatment number is relative to the given timepoint, where each week has 4 scheduled treatments.

^b URR is calculated as (Pre-Post BUN)/(Pre BUN).

STATKING Clinical Services (month day, year)

Source Program: xxxxxxxx.sas

Only selected time points and treatment numbers are shown on this mock table. The final table will display all time points (Weeks 2-9 for In-Center and Weeks 10-19 for In-Home) and all four treatment numbers within each time point.

Table 34. Summary Table of Clinically Significant Alarms
 Outset Medical - Study No. 2014-01
 ITT Population (N=xxx)

Alarm Type	Treatment Period ^a	
	In-Center	In-Home
Air in Venous Lines	xxx (xxx%)	xxx (xxx%)
Low Systolic Blood Pressure	xxx (xxx%)	xxx (xxx%)
High Venous Pressure	xxx (xxx%)	xxx (xxx%)
Low Venous Pressure	xxx (xxx%)	xxx (xxx%)
Blood Leak in Dialyzer	xxx (xxx%)	xxx (xxx%)
Alarms that End Treatment	xxx (xxx%)	xxx (xxx%)

^a Summaries per treatment period are the number and percentage of treatments with the respective alarm type. The denominator is the number of treatments for all ITT population subjects during the treatment period.
 STATKING Clinical Services (month day, year)
 Source Program: xxxxxxxx.sas

Table 35. Clinically Significant Alarms Summary Statistics
 Outset Medical - Study No. 2014-01
 ITT Population (N=xxx)

Alarm Type=xxxxxxxxxxxxxxxx

Treatment Period	Time Point	Treatment Number ^a	Mean	Std Dev	n	Min	Max	Median
N/A	Week 1	1	xxx	xxx	xxx	xxx	xxx	xxx
In-Center	Week 9	4	xxx	xxx	xxx	xxx	xxx	xxx
In-Home	Week 19	4	xxx	xxx	xxx	xxx	xxx	xxx

^a Treatment number is relative to the given timepoint, where each week has 4 scheduled treatments.
 STATKING Clinical Services (month day, year)
 Source Program: xxxxxxxx.sas

Only selected time points and treatment numbers are shown on this mock table. The final table will display all time points (Weeks 2-9 for In-Center and Weeks 10-19 for In-Home) and all four treatment numbers within each time point. The format of this table will be repeated for alarm type.

Table 40. Time to Resolve/Clear Alarms Summary Statistics
 Outset Medical - Study No. 2014-01
 ITT Population (N=xxx)

Treatment Period	Mean	Std Dev	n	Min	Max	Median
N/A	xxx	xxx	xxx	xxx	xxx	xxx
In-Center	xxx	xxx	xxx	xxx	xxx	xxx
In-Home	xxx	xxx	xxx	xxx	xxx	xxx

STATKING Clinical Services (month day, year)
 Source Program: xxxxxxxx.sas

Table 41. Prescription Changes Summary Statistics - Overall
 Outset Medical - Study No. 2014-01
 ITT Population (N=xxx)

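### SAP Tables 33 and 35–39 set In-Home as Weeks 10–19, which does not fit the SAP's own 21-week schedule

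*SAP*

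**What the plan says.** SAP 1.1 states the overall length, "Subjects will be enrolled in the trial for approximately 21 weeks", and lists four separate periods. These are a 1-week run-in; Treatment 1 In-Center with 32 treatments over about 8 weeks; the In-Home Transition, in which subjects "perform self-care dialysis 4 times/week for approximately 4 weeks"; and Treatment 2 In-Home. On the last, SAP 1.2 says: "This In-Home treatment period lasts a total of 32 treatments (approximately 8 weeks, with 4 treatments/week"). SAP 1.2 also says that in the transition the subject or care partner sets up and starts therapy "under the supervision of study personnel In-Center during the first portion", and that the second portion takes place at home.

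BUN is drawn once a week in every period. SAP 1.2 lists "Weekly: concomitant medications and pre and post BUN sample collection", and the row for "Pre and Post BUN sample collection" in Protocol Appendix B carries 21 weekly marks.

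In SAP Appendix B, Tables 33 and 35 put Week 1 outside both treatment periods, and Table 41 labels it as baseline. The footnotes to Tables 33 and 35 fix four scheduled treatments per week. The mock In-Home row in both is Week 19, and the notes beneath give the ranges: "The final table will display all time points (Weeks 2-9 for In-Center and Weeks 10-19 for In-Home"). Neither table has a transition row.

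On adverse events, Protocol 11.6 sorts all study-emergent events into In-Center or In-Home. SAP Tables 17–21 have In-Center, In-Home and Overall columns. The footnotes to Tables 17, 19 and 21 count an event by its start date within the period; Tables 18 and 20 carry only a denominator footnote.

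**The concern.** The notes get the In-Center weeks exactly right and then run In-Home straight on from week 10, as if there were no transition, for two weeks longer than the home period lasts. Followed as written, the In-Home rows would begin with training sessions, some of them supervised in the center, and would stop before the home period ends.

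Tables 33 and 35–39 are the listed tables that show BUN and alarms week by week. A reader would use them to see whether dialysis adequacy and alarm frequency hold steady as subjects move to unsupervised home use. Rows that mix training into In-Home and lose the final home weeks blur that picture. SAP Appendix A commits the deliverable tables to the mock format, so the error is best removed before programming.

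**Working it through.** **Inputs.** Run-in 1 week, In-Center 8 weeks, transition about 4 weeks, In-Home 8 weeks, total about 21 weeks, 4 treatments per week (all SAP 1.1). In-Home range Weeks 10–19 (notes to Tables 33 and 35).

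**Reproducing the plan's total.** 1 + 8 + 4 + 8 = 21 weeks, which agrees with SAP 1.1 and with the 21 BUN marks in Protocol Appendix B.

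**Week positions, with week 1 as the run-in.**
- In-Center: weeks 2–9, as in the notes.
- Transition: weeks 10–13.
- In-Home: weeks 14–21, that is 8 × 4 = 32 treatments, as in SAP 1.1.

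**The range in the notes.** Weeks 10–19 is 19 − 10 + 1 = 10 weeks, or 10 × 4 = 40 scheduled treatments, against 32 in Treatment Period 2. The calendar in the notes ends at 1 + 8 + 10 = 19 weeks, not 21.

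**Overlap at the nominal schedule.**
- Labelled In-Home but transition: weeks 10–13, 4 of 10 (40%), 16 treatments.
- Correctly labelled: weeks 14–19, 6 of 8 home weeks, 24 treatments.
- Home weeks not displayed: weeks 20–21, 2 of 8 (25%), 8 treatments.

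At one BUN pair a week, that is about 4 transition pairs per subject shown as In-Home and about 2 of 8 home pairs left out.

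**Other transition lengths.** For a transition of T weeks, transition is weeks 10 to 9 + T and home is weeks 10 + T to 17 + T. The documents give only about 4 weeks; the other values of T are assumptions used to test the range.

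| T | Home weeks | Transition weeks among the 10 labelled In-Home | Home weeks outside 10–19 |
|---|---|---|---|
| 0 | 10–17 | 0 (range 2 weeks too long) | 0 of 8 |
| 2 | 12–19 | 2 (20%) | 0 of 8 |
| 3 | 13–20 | 3 (30%) | 1 of 8 (12.5%) |
| 4 | 14–21 | 4 (40%) | 2 of 8 (25%) |
| 5 | 15–22 | 5 (50%) | 3 of 8 (37.5%) |

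No row gives a home period of weeks 10–19, since 10 weeks cannot equal 8. Pooling the transition with home at T = 4 gives weeks 10–21, so that reading does not produce the stated range either.

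**The case against.** The strongest defence is that the note is an instruction to the programmer, placed below the mock table, and is not a printed footnote. It asks for all time points. The SAP defines each treatment period by 32 treatments, not by calendar week, and Tables 23, 24, 32 and 41 use Treatments 1–16 and 17–32. A programmer working from a period variable would probably notice the mismatch. This stands in part: the 4-of-10 and 2-of-8 figures are conditional on the range being used as a calendar rule. It does not rescue the text. The range is stated, the mock rows repeat Week 19, and adding weeks 20–21 would still leave the transition labelled In-Home.

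A second defence is that the lengths are approximate and subjects drift. After lost contact, for example, "study treatments will resume at the point when the last treatment was conducted" (Protocol 7.6). That is true, and the exact split will vary by subject. It argues against fixed calendar weeks as the definition of a period, so it supports numbering weeks within period.

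A third is that the mislabelling is partial, because the second portion of the transition is at home. This also stands. The 4 weeks are transition weeks, not weeks all treated in the wrong setting, and the length of the In-Center portion is not given.

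A reader might go further and infer that the primary results are contaminated. The documents do not support that. Protocol 6.1 restricts the primary endpoints to Treatment Periods 1 and 2, the primary tables carry no such week range, and nothing in the SAP says that this range defines the model's period or week terms. Table 34 counts alarms over all treatments in each period.

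A reader might also infer that the range is left over from a 2-week transition, since 2 + 8 weeks from week 10 ends at week 19. The fit is suggestive, but the documents reviewed do not say so.

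Finally, the split in Protocol 11.6 might be read as an error that moves adverse events between columns. Protocol 9.2.1 and SAP 5.2 both summarize by treatment period. The footnotes to Tables 17, 19 and 21 already keep transition events out of both period columns, and SAP 5.1 implies that Overall includes them. This is a gap in clarity. Under the nominal schedule the transition holds 16 of 32 + 16 + 32 = 80 post-enrolment treatments (20%), but that is a share of treatments, not a rate of misplaced events.

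**Conclusion.** The In-Home week range in the notes and mock rows of Tables 33 and 35, carried into Tables 36–39, contradicts the SAP's own schedule. The arithmetic is certain: 10 weeks against 8, whatever the transition length. The consequence is conditional. If the range is applied as a calendar rule and the transition lasts 4 weeks, 4 of the 10 In-Home weeks are transition weeks and 2 of the 8 home weeks are missing. If the transition runs 3 to 5 weeks (an assumption), these become 3 to 5 of 10 and 1 to 3 of 8.

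Severity is minor, because only descriptive tables of BUN and alarms are touched. The handling of transition adverse events merits an optional clarifying sentence and is not an error on its own. Which adverse event counts would change, and by how much, cannot be stated from the documents.

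**What to change.** In the notes and shells of Tables 33 and 35–39, define rows by study period and number the weeks within it: In-Center weeks 1–8, and In-Home weeks 1–8 (nominally study weeks 14–21). Either show the transition (nominally study weeks 10–13) as a separate block not labelled In-Home, or state that it is excluded. Either choice cures the contradiction.

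Optionally, add one SAP sentence saying that adverse events with onset in the transition are counted in neither period column of Tables 17–21 but are included in Overall. For Tables 18 and 20, use the Table 21 type of start-date wording. The footnotes to Tables 17 and 19 also refer to the treatment interval, and Tables 18 and 20 have no interval rows. Align Protocol 11.6 when the protocol is next amended. Table 16 and the primary analyses stay as they are.

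The cost is a few edits to SAP notes, shells and footnotes, with no new data, because BUN and adverse events are already scheduled in the transition and the console reports alarms. It is best done before the tables are programmed, since SAP Appendix A makes format changes after SAP approval chargeable. The Protocol 11.6 wording needs a written amendment under Protocol 14.4 and can wait.
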